## DATA ANALYSIS

In order to analyze the data, we consulted a statistician from the UCSF Clinical and Translational Science Institute (CTSI). The statistician analyzed the entire data set using statistical software. Demographic characteristics of each group were assessed to see if there were obvious disproportionate distributions of certain characteristics in the groups which may have affected the adherence. Medication adherence for each medication was calculated as a percentage of the total number of doses received during the study period divided by the total number of doses prescribed. As a result, this percentage ranged from 0 to 100. Medication adherence percentages and asthma symptom control scores during both the run-in and intervention periods were measured and the differences between the two time periods (Adherence Delta  $\Delta$  and asthma symptom control Delta) was calculated for each patient. For objectives 1 & 2, we compared the mean “adherence delta” and “asthma symptom control delta” for each group using a student t-test.

Finally for the third objective, in order to assess if there were specific patient behavior characteristics which were associated with the success of a novel asthma medication reminder system, we identified those patients whose adherence rates increased from baseline. We compared the scores of the RAM Scale for those patients with a change in adherence compared to those patients with no improvement in adherence. We used a chi-squared test to assess if the RAM scores which suggest 'forgetful nonadherence' were associated with improved adherence rates during exposure to the reminder system. Analyses were performed using SAS version 9.4 (SAS Institute, Cary, NC).

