## COVER PAGE

Study Title	Interventions To Help Asthma Clinical Adherence (ITHACA)
NCT Number	NCT02999789
Document Description	Statistical Analysis Plan
Document Date	23 February 2021

This study was a quasi-experimental single-center pilot trial that used a staggered implementation design which measured the effect of an asthma medication reminder system device on asthma controller medication adherence during an initial run-in period and an intervention period. Because the intervention was a reminder system, it was not possible to 'blind' the participants.

For the pilot phase, we aimed to recruit children ages 5 to 17 years with a diagnosis of persistent asthma who required a daily inhaled corticosteroid metered dose inhaler and whose guardian was the person responsible for directly administering or supervising the administration of their daily asthma medication. Our target sample size at the study's onset was to recruit 30 children ages 5 to 17. The sample size was limited by the budget limitations. Based on cost-efficiency and limitations, 30 participants would give a general estimate of the effectiveness of this intervention. The study results could be used for the power calculations for a future, larger RCT. Assuming a positive effect of reminder systems and a baseline adherence rate of 60%, with 15 patients in each group, with a power of 0.80, an alpha of 0.05, there would be enough power to detect a 15% change in adherence which is within the range of improvement reported. This percentage change translated to a Number Needed to Treat (NNT) of 6 patients.

We only recruited from a University-affiliated clinic serving publicly insured children. We recruited children whose asthma subspecialist or health care provider practiced at the Children's Health Center (CHC) at Zuckerberg San Francisco General Hospital. We only recruited from the primary care clinics and the asthma clinic. We only recruited children whose guardian responsible for administering their daily asthma medication had Limited English Proficiency (LEP) and whose primary language was Spanish. Lastly, we only included children whose daily inhaled corticosteroid was a metered dose inhaler (MDI) that was either Flovent (fluticasone propionate) HFA (Hydrofluoroalkane) or Qvar (beclomethasone dipropionate) HFA. This was the case because the SmartInhaler device was only available for those two MDIs.

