The final step prior to the end of the initial visit was giving the participant and guardian the SmartInhaler device. Participants received either a Flovent or a Qvar SmartInhaler device depending on which daily controller medication they were taking. The SmartInhaler device unobtrusively would record every time the asthma daily medication is taken and communicate this information to the study center.

If the activated reminder system was activated and the participant did not take their daily medication, the SmartInhaler would send a text message to the patient's cell phone in Spanish reminding them to take their daily medication. Only the Flovent SmartInhaler featured an additional audio-visual reminder on the device that could also remind study participants to take their missed medication. Due to the Flovent SmartInhaler's additional feature reminding patients, participants were stratified into two groups according to the type of SmartInhaler they were using. The aim was to recruit 15 participants to use the Flovent SmartInhaler and 15 participants to use the Qvar SmartInhaler.

Data regarding daily asthma medication adherence was obtained using the SmartInhaler. Medication adherence for each medication would be calculated as a percentage of total number of doses received during the study period divided by the total number of doses prescribed. As a result, the percentage ranged from 0 to 100. The activated reminder system was initially deactivated but the SmartInhaler was turned on since it was going to be measure baseline adherence. A power cord given to the participants and guardians so they could recharge the battery of the SmartInhaler when it became depleted. The guardians of the participants were compensated with a \$20 gift card for their time. The ACT, RAM, PAQLQ, PACQLQ, and PAMSE were completed at every study visit.

The time interval between visit 1 and visit 2 was the run-in period. During the run-in period, we determined baseline daily asthma controller medication rates using the SmartInhaler system without the activated reminder system and we also assessed baseline asthma symptom control.

**Figure 1:** Study Design and Events for Each Visit (ACT = Asthma Control Test; RAM = Reported Adherence Medication Scale)

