During visit 2, participants were randomized by a block design to ensure participants were equally distributed among both study groups. The University’s Clinical and Translational Science Institute was consulted to assist in creating the randomization through computer generated random numbers. Once those numbers were generated, they were placed in envelopes by non-study personnel. A staggered implementation design was implemented in order to offer the intervention to all participants. Half the patients were randomly selected to have the reminder system activated during this 2nd visit. The reminder system was activated and data regarding daily asthma medication adherence was obtained using the SmartInhaler and sent to the data center. The other half did not have the reminder system activated in order to provide for a concurrent control group. That group had delayed activation until the 3rd visit.

During the 3rd visit, the rest of the participants had the reminder system activated. As for the group that had the SmartInhaler reminder system activated at the 2nd visit, we collected the SmartInhaler devices and administered a modified version of the Technology Acceptance Model (TAM) questionnaire which collects patient feedback about the device’s usefulness. The TAM determines the user acceptance of any technology perceived usefulness and perceived ease of use factors. The TAM questionnaire, first developed by Davis (1993) and validated in different contexts by several researchers (Nair & Das, 2011), consisted of 17 questions, of which 13 were on a 5-point Likert-type scale questionnaire, with the scale ranging from 1 (strongly agree) to 5 (strongly disagree). A modified version of this questionnaire was used for this study. For the delayed activation group, their final visit was their 4th visit. At that final visit, we collected the SmartInhaler devices and obtain patient feedback on its usefulness by administering the TAM.

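### Does the lack of visit limits for the delayed arm's intervention period leave the comparison for objectives 1 and 2 undefined?

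*SAP*

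**What the plan says.** The study description in the SAP (under COVER PAGE) speaks of adherence measured "during an initial run-in period and an intervention period". It limits the first of these: "The time interval between visit 1 and visit 2 was the run-in period". The readable text gives no such limits for the second.

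Patients are randomized at visit 2. Half have the reminder switched on then. For the rest: "The other half did not have the reminder system activated in order to provide for a concurrent control group". At visit 3 the immediate arm hands back its devices and "the rest of the participants had the reminder system activated". The delayed arm finishes at visit 4.

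DATA ANALYSIS takes adherence and symptom-control values "during both the run-in and intervention periods were measured and the differences between the two time periods" to give one delta of each kind per patient. For objectives 1 and 2 it compares the mean deltas "for each group using a student t-test".

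**The concern.** A delta built from two periods is applied to an arm that has three. In the immediate arm only one window follows run-in, so nothing is open. In the delayed arm the second term could be the reminder-off window, the reminder-on window, or both together.

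Some wording could lead an analyst away from the reminder-off window. The design paragraph uses the word intervention for the activated reminder itself: "A staggered implementation design was implemented in order to offer the intervention to all participants". In the delayed arm that exists only after visit 3. Objective 3 concerns adherence while exposed to the reminder, which in that arm again means visits 3 to 4. The adherence formula counts doses over the study period without naming visits. The word group also has two uses, since "participants were stratified into two groups according to the type of SmartInhaler they were using".

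Objectives 1 and 2 both rest on this contrast, and the SAP says the results could feed the power calculation of a larger trial. A diluted or empty contrast would carry forward into that calculation.

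**Working it through.** **What each reading would give.** The inputs from the study description are 15 patients per group, power 0.80, alpha 0.05 and a 15% change, taken here as 15 points. The following are assumed: a two-sided test, the same reminder effect in both arms, and no time trend. The readable text gives neither an SD nor interval lengths.

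Without an SD the stated power of 0.80 cannot be reproduced, so the SD was solved backwards. For a t-test with 2 × 15 − 2 = 28 degrees of freedom, the noncentrality is d / (SD × √(2/n)). Power of 0.80 at d = 15 needs an SD of the delta of about 14.15: 15 / (14.15 × √(2/15)) = 15 / 5.17 = 2.90.

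Let f be the share of the delayed arm's chosen window spent with the reminder off. The immediate arm's expected delta is 15 and the delayed arm's is 15(1 − f), so the expected difference is 15 − 15(1 − f) = 15f.

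| Delayed arm's window | f | Expected difference (points) | Power, SD 14.15 | Power, SD 20 |
|---|---|---|---|---|
| Visits 2–3 | 1 | 15 | 0.80 | 0.51 |
| Visits 2–4, equal intervals | 1/2 | 7.5 | 0.29 | 0.17 |
| Visits 3–4 | 0 | 0 | 0.05 | 0.05 |

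With unequal intervals the pooled reading gives 10 points (f = 2/3, power 0.46) or 5 points (f = 1/3, power 0.15) at SD 14.15. The table holds the SD equal in both arms. If pooling two periods is allowed to lower the delayed arm's SD (between-period correlation 0.5, so 14.15 × √0.75 = 12.25), the 0.29 becomes 0.32. If adherence drifts by −5 points in visits 3 to 4, the visits 3–4 reading gives 15 − (15 − 5) = 5, while the visits 2–3 reading stays at 15.

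**Which reading the design allows.** Setting the windows side by side:

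| Window | Immediate arm | Delayed arm |
|---|---|---|
| Visits 1–2 | run-in, reminder off | run-in, reminder off |
| Visits 2–3 | reminder on, device collected at visit 3 | reminder off |
| Visits 3–4 | no device data | reminder on, device collected at visit 4 |

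1. Visits 2–3 are the only window after run-in in which both arms have device data.
2. The stated purpose of the delay is a concurrent control. With visits 3–4 the delayed arm would be neither concurrent nor a control. With visits 2–4 it would be a control for only part of the time.
3. The symptom-control delta follows the same logic. Scores are taken at every visit, and visit 3 closes the shared window, before the delayed arm is activated. Whether visit 1 or visit 2 supplies the baseline is not stated, but both scores come before any activation (taking the visit 2 score as obtained before the device is switched on). The choice therefore does not bias the comparison of randomized arms.
4. For the word group, the visit 2 paragraph speaks of both study groups when it describes randomization. Device type is introduced as a stratification. A t-test of Flovent against Qvar users would set the randomization aside.
5. Objective 3 is described in its own terms, as a rise from baseline during exposure to the reminder. The text does not say that the delta of objective 1 is reused there, so no single delta has to serve both purposes.

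**The case for a change.** The best case for a change is that defining the analysed contrast is the SAP's own job and cannot be left to the protocol. DATA ANALYSIS never adopts the visits 2–3 window explicitly, and a literal reader who equates intervention with the activated reminder arrives at visits 3–4. Between the best and worst readings the estimate runs from 15 points to 0, and that ordering does not depend on the assumed SD. Naming the visits would take a few sentences and no new data.

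Part of this stands. The visit limits are not written in the readable text, and the SAP would be clearer with them. The arithmetic is also right under its assumptions. However, it shows the cost of misreading the design and not what the plan would be expected to produce. Both weaker readings require the analyst to overlook the declared purpose of the control group. The study design figure, captioned as showing the events at each visit, is not shown here and may label the periods. The document is also written largely in the past tense and reports that the statistician analysed the full data set. Prescribing a window now could not show which one was used, and might misdescribe it.

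**Conclusion.** The concern does not call for a change. The SAP leaves the delayed arm's second window unnamed, but its own design description points to visits 2 to 3, which is what a competent analyst would use. On that reading the comparison of mean deltas between the randomized arms is sound. It keeps the full 15-point effect, with power 0.80 at the back-solved SD of 14.15, and nothing is lost to dilution. The figures of 7.5 and 0 points belong to readings that defeat the staggered design, and they also rest on assumed equal intervals, no time trend and a common reminder effect. This conclusion depends on taking the concurrent-control sentence at face value and the randomized arms as the groups compared.

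### The t-test on deltas is valid for the randomised arms over visits 2–3, but adjusting for the run-in value is usually more precise; the plan should add that model and name the arm and interval

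*SAP*

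**What the plan says.** The SAP's DATA ANALYSIS section takes adherence and symptom control "during both the run-in and intervention periods were measured and the differences between the two time periods", forms one delta per child, and compares the mean deltas "for each group using a student t-test". No model with the run-in value as a covariate is given. The section does not define group, nor the intervention period of the delayed arm.

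The design is described earlier, under COVER PAGE:
- Run-in is visit 1 to visit 2, when "we determined baseline daily asthma controller medication rates using the SmartInhaler system without the activated reminder system" "and we also assessed baseline asthma symptom control". Symptom scores recur: "The ACT, RAM, PAQLQ, PACQLQ, and PAMSE were completed at every study visit".
- "During visit 2, participants were randomized by a block design". Half had reminders switched on then. "The other half did not have the reminder system activated in order to provide for a concurrent control group".
- At visit 3 "the rest of the participants had the reminder system activated". The delayed arm then continued to visit 4.
- The two inhaler types are also called groups, in the text on stratification by device.

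**The concern.** The run-in value is measured before randomisation and is likely to predict the later value. Subtracting it fixes its coefficient at 1. Unless the true slope is near 1, this adds noise that a fitted slope would remove. With about 30 children and results that the SAP says could feed the power calculation of a larger trial, the width of the interval matters.

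The wording adds a second, smaller issue. The delayed arm has two post-run-in intervals: visits 2–3 with reminders off and visits 3–4 with reminders on. Only the first gives a contrast with the immediate arm. Because DATA ANALYSIS does not name the interval, an analyst could take the wrong one, and baseline adjustment would not repair that.

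**Working it through.** **Inputs from the SAP.** 15 per group, alpha 0.05, power 0.80, baseline adherence 60%, a 15% change (read as 15 points), adherence as a per-child percentage from 0 to 100, and a symptom score from 0 to 27. The SAP gives no SD and no correlation (rho) between run-in and later values. Both are assumptions below, shown over a range.

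**The plan's own figure.** For a two-sided t-test on deltas, 15 per arm gives 80% power for 15 points only if the SD of the delta is about 14.2 (noncentral t). The normal approximation gives 15 / [(1.96 + 0.84) × √(2/15)] ≈ 14.7. The SAP states no SD, so its figure cannot be confirmed on this scale. Read as two proportions, 0.60 against 0.75, 15 per arm gives about 14% power. That is a separate matter from the present point.

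**Variance.** With equal period SD s:
- change score: 2s²(1 − rho)
- baseline-adjusted: s²(1 − rho²)
- ratio, adjusted to change: (1 + rho)/2, that is 0.65, 0.75, 0.85 and 0.95 at rho 0.3, 0.5, 0.7 and 0.9

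Estimating the slope with 30 children multiplies the ratio by 1 + 1/26, giving 0.675, 0.779, 0.883 and 0.987. At rho 0.95 it is 1.012. Break-even is at rho of about 0.93.

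**Power and precision for adherence.** 15 per arm, SD 20, 15-point effect, randomised arms over visits 2–3, 20,000 simulated trials per setting. Each cell gives t-test on deltas / baseline-adjusted; half-widths use unrounded standard errors.

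| rho | Power | Mean SE | 95% CI half-width (points) |
|---|---|---|---|
| 0.3 | 39% / 53% | 8.57 / 7.03 | 17.5 / 14.4 |
| 0.5 | 51% / 61% | 7.24 / 6.39 | 14.8 / 13.1 |
| 0.7 | 73% / 78% | 5.60 / 5.26 | 11.5 / 10.8 |
| 0.9 | 99% / 99% | 3.23 / 3.21 | 6.6 / 6.6 |

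Noncentral-t power agrees to within rounding. Under no effect, both methods reject in about 5% of trials.

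**Sensitivity.**
- SD 25: 26% / 37%, 36% / 44%, 54% / 59%, 94% / 94%.
- Delta SD held at 14.17, where the t-test has about 80% power: the adjusted test reaches 92.5%, 88.6%, 84.5% and 80.3% at rho 0.3 to 0.9, and 79.3% at rho 0.95.
- Slope near 1 (run-in SD 18, later SD 25, rho 0.7; slope 0.7 × 25/18 = 0.97): change variance 324 + 625 − 630 = 319, adjusted variance 625 × 0.51 = 319. Simulated power is 60% / 58%, a small loss.

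**Objective 2.** An assumed SD of 4 scales the half-widths by 4/20: 3.5 / 2.9, 3.0 / 2.6, 2.3 / 2.2 and 1.3 / 1.3 score points.

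**The interval.** If the delayed arm's delta used visits 3–4 and reminders raised adherence by 15 points in both arms, the expected arm difference would be 15 − 15 = 0. In simulation both methods then reject in 5.0% to 5.2% of trials.

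**The case against.** The best reply is that a t-test on change from run-in is simple, unbiased and correctly sized on the randomised visit 2–3 contrast, and suits a budget-limited pilot of 30 children seeking a general estimate. This stands: the adjustment gains precision and corrects no error.

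The size of the gain is also open. If the SAP's 80% power refers to a t-test on deltas and the period SD is 20, the implied rho is about 0.75. Simulated power there is 79.9% against 83.5%, and the half-width about 10.5 against 10.0 points. Lower correlations give more, higher ones nothing. This stands too, and is why a range is shown.

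A reader might infer that the SAP compares two exposed arms, or the two inhaler types, so that its main test cannot estimate the reminder effect. The document does not support that. It randomises children into two study groups and says why half were left without reminders: "The other half did not have the reminder system activated in order to provide for a concurrent control group". That purpose is met only by the arm contrast over visits 2–3. The zero difference on the visit 3–4 reading follows by construction and is no evidence of what was intended. What remains is that DATA ANALYSIS does not say so itself, while its third objective speaks of exposure to the reminder, which for the delayed arm begins only at visit 3.

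Finally, the section is written in the past tense, so the model may come after the analysis. That affects its label, not its use.

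**Conclusion.** The point holds as one of efficiency, with a clarification attached. On the reading that the design implies, the delta t-test is valid, and it is usually less precise than a baseline-adjusted comparison. At 15 per arm and SD 20 the gain is about 14, 10 and 5 percentage points of power at rho 0.3, 0.5 and 0.7. It disappears near rho 0.9, and there can be a loss of 1–2 points at higher correlations or a slope near 1. All these sizes rest on assumed SDs and correlations; only the 15-point effect and the 15 per group are the SAP's. It would go too far to call the planned test invalid, or to say that the SAP intends the visit 3–4 comparison.

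**What to change.** For objectives 1 and 2, add a linear model of the concurrent-period outcome on randomised arm and the pre-randomisation value:
- Adherence: visit 2–3 adherence on arm and run-in adherence.
- Symptom control: visit 3 score on arm and the score at or before visit 2. A later score must not be a covariate; in the delayed arm the last score before activation can be the visit 3 outcome itself.

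Report the adjusted arm difference with its 95% CI beside the delta t-test. In the same sentence, state that group means randomised arm and that the delayed arm's delta runs from run-in to visits 2–3. If the analysis is already done, label the model as added later.

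Device type may be an optional prognostic term. It removes the shift from chance device imbalance: with an assumed 10-point device difference and devices split 8/7 and 7/8 between the arms, that shift is 10 × (8/15 − 7/15) = 0.67 points, in either direction. It also narrows the interval if device affects adherence; in that setting at rho 0.5 the SE falls from 6.65 to 6.39.

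The cost is SAP wording, one model on data already collected, one of 28 residual degrees of freedom (two with device), and about 0 to 2 points of power if the terms do not help.

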be to lead recruitment and retention of patients, collect data, conduct follow-up visits and oversee day-to-day study tasks.

[figure not shown]
A summary of the different events at each visit is detailed in **Figure 2**. After consent was obtained from both the child and caregiver, we collected demographic data on the child (e.g., age, gender, age of asthma diagnosis, occupation, languages spoken at home, relatives with asthma, smoking exposure) and the characteristics of the patient's disease (e.g., severity, medications used, previous hospitalizations, current provider, subspecialty provider for asthma [if any], duration of use of current medications) which may affect adherence to their medication or asthma symptom control. The subject's guardian then completed a few surveys including the Pediatric Asthma Quality of Life Questionnaire (PAQLQ), the Pediatric Asthma Caregiver Quality of Life Questionnaire (PACQLQ), the Parent Asthma Management Self-efficacy (PAMSE) scale and a survey that included self-described medication taking behavior and a decision-making survey (a modified Reported Adherence to Medication (RAM) Survey). The RAM Survey, is a 3 question instrument, which helps describe and predict potential types of nonadherence behavior. The PAQLQ is an asthma-specific quality of life scale that has been validated in children and adolescents aged seven to 17 years and it has officially been translated into Spanish (Juniper, 1996). The PACQLQ is an asthma-specific quality of life scale for caregivers of children with asthma. (Juniper, 1996). The PAMSE measures parental self-efficacy for the management and prevention of acute asthma exacerbations. (Bursch, 1996) Since the RAM survey and PAMSE scale are available in English only, they were translated into Spanish using a systematic approach (Brislin, Lonner & Thorndike, 1973). The child's guardian also completed the Childhood Asthma Control Test (C-ACT). Although the C-ACT is used only for patients ages 4 to 11, we used this for children older than 11 because this version is only to be filled out by the parent or guardian. The C-ACT is a 7 item scale, with scores ranging from 0 (poor asthma control) to 27 (complete asthma control). In general, a C-ACT score >19 indicates well-controlled asthma.

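### Objective 3 counts children with little or no room to improve as non-improvers and ignores run-in adherence, which can bias the comparison by RAM type

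*SAP*

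**What the plan says.** Under DATA ANALYSIS, the SAP defines success for objective 3 as any rise: "we identified those patients whose adherence rates increased from baseline". RAM scores are then compared "for those patients with a change in adherence compared to those patients with no improvement in adherence", and the test is fixed as "We used a chi-squared test to assess if the RAM scores which suggest 'forgetful nonadherence' were associated with improved adherence rates". The adherence measure is bounded: "As a result, this percentage ranged from 0 to 100". No eligibility criterion in the SAP requires missed doses in run-in. Objective 3 neither sets fully adherent children apart nor adjusts for run-in adherence.

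Three statements in the earlier text, under the COVER PAGE heading, bear on this:
- The RAM survey is a three-question instrument "which helps describe and predict potential types of nonadherence behavior".
- The reminder is sent on a missed dose: "If the activated reminder system was activated and the participant did not take their daily medication, the SmartInhaler would send a text message".
- RAM is repeated: "The ACT, RAM, PAQLQ, PACQLQ, and PAMSE were completed at every study visit". Objective 3 does not name the visit whose score is used.

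**The concern.** Objective 3 asks whether forgetful non-adherence responds to reminders better than other kinds. That question has meaning only for children who miss doses. The rule nevertheless places every child with a run-in value of 100% in the non-improved group, whatever the reminder does, and places most children just below 100% there too.

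If guardians of such children less often report forgetting, the children gather in the cell for not forgetful and not improved. The test would then favour its own hypothesis for a reason unrelated to the reminder. The SAP says that the results could inform a larger trial, so a spurious signal about who benefits could mislead that design.

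**Working it through.** **Inputs.** From the SAP: success is any rise, the scale stops at 100, 30 children are planned, baseline adherence is taken as 60%, and the test is chi-squared. The SAP gives no figure for objective 3 that could be reproduced; its power statement concerns a 15% change in adherence. Assumed, because the SAP does not give them: the spread of run-in adherence, the number of run-in doses, the share scored forgetful, and the chance of a rise.

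**1. The rule.** Delta = intervention adherence − run-in adherence. With run-in = 100 and a maximum of 100, delta ≤ 0, so the child can only be a non-improver.

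**2. When this creates an association.** Let s be the share of children at ceiling, f0 and f1 the forgetful share among ceiling children and the others, and p the chance of a rise for any child with room, the same for every RAM type.

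- Improved among forgetful = (1−s)·f1·p / [s·f0 + (1−s)·f1]
- Improved among not forgetful = (1−s)(1−f1)·p / [s(1−f0) + (1−s)(1−f1)]

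If f0 = f1, both equal (1−s)·p and the odds ratio is 1. With s = 0.20, f0 = 0.10, f1 = 0.60 and p = 0.70 they are 0.336/0.50 = 67.2% and 0.224/0.50 = 44.8%, an odds ratio of 2.52 with no true difference by type.

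Simulated rejection (30 children, 40,000 trials, uncorrected test at 0.05), ranges for p = 0.50 to 0.70:

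| At ceiling | Forgetful, ceiling v others | Odds ratio | Rejection |
|---|---|---|---|
| any share up to 30% | 50% v 50% | 1.0 | about 5% |
| 10% | 10% v 60% | 1.45–1.73 | 7–11% |
| 20% | 10% v 60% | 1.96–2.52 | 14–23% |
| 30% | 10% v 60% | 2.56–3.40 | 22–36% |

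**3. How many children at exactly 100%?** With a beta-binomial model, mean 60% and 30 run-in doses, the expected number among 30 children is 0.05 at a between-child SD of 15 points, 0.3 at 20, 1.1 at 25 and 2.8 at 30. More doses lower it.

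**4. Sensitivity to where they fall.** Exact calculation with 12 forgetful and 18 not-forgetful children and a 70% chance of a rise for each child with room:

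| At ceiling | None of them forgetful | One of them forgetful |
|---|---|---|
| 0 | 4.9% | – |
| 1 | 4.7% | – |
| 2 | 5.7% | – |
| 3 | 7.7% | 2.8% |
| 6 | 20.3% | 6.7% |
| 9 | 45.3% | 21.8% |

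For 6 at ceiling and none forgetful, the improved rates are 70% and 0.70 × 12/18 = 47%.

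**5. Near-ceiling children.** Simulation with mean adherence 60%, 30 doses in each period, and a reminder that recovers 15% of missed doses for every RAM type. Near ceiling means run-in adherence of 90% or more.

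| SD (points) | Near ceiling | Rejection, forgetful 30% v 70% | Rejection, 10% v 70% |
|---|---|---|---|
| 20 | 9% | 7% | 8% |
| 25 | 17% | 9% | 13–14% |
| 30 | 25% | 12–13% | 21% |

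At SD 25, near-ceiling children improve 28% of the time and the rest 70%. With no RAM contrast, rejection is about 5% at every SD.

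**6. Does the remedy work?** In the setting of step 5, dropping only children at exactly 100% leaves rejection as high as 9.6% (SD 30, 10% v 70%). A linear regression of delta on RAM type and run-in adherence, keeping all children, rejects in about 5% to 6% of trials throughout. In that simulation the reminder effect is linear in adherence, which suits the model.

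**The case against.** The strongest reply is that the bias needs two conditions that the SAP does not establish: a fair number of children at or near 100%, and a lower forgetful share among them. At the planned 60% baseline, children at exactly 100% should be few, and step 4 shows that moving a single child can bring 20% rejection back to about 7%. The RAM cut-off and its relation to recorded doses are not given. This stands, and it limits the size of the point. It does not remove the rule's fault, because near-ceiling children are more numerous and also seldom rise.

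A reader might infer that children with perfect run-in adherence never receive a reminder. The SAP does not support that: the trigger is a dose missed once the system is active ("If the activated reminder system was activated and the participant did not take their daily medication"), so a child who is perfect in run-in and later misses a dose is reminded. Only a child who stays fully adherent gets none.

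The groups as worded could also overlap, since a child whose adherence falls has both changed and not improved. The neighbouring sentences speak of adherence that increased or improved, so the intended split can be recovered. This, like the unnamed RAM visit, is loose wording that should be tidied and does not carry the point.

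**Conclusion.** The concern holds in a conditional form. The classification puts children who cannot rise, and most of those who can barely rise, among the non-improvers, and nothing in objective 3 conditions on run-in adherence. It would be too strong to say that the rule builds in an association with forgetful RAM; it permits one if ceiling children are less often scored forgetful.

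Under the plan's 60% baseline and an assumed SD of 20 to 30 points, the false-positive rate is roughly 5% to 13% for no to moderate RAM contrast. It is near 5% when only one or two children are at exactly 100%. Rates of 20% or more need about a fifth or more of the children at or near the ceiling, with all or nearly all of them not forgetful. For an exploratory objective in a 30-child pilot, this is a cheap improvement and not a threat to the main comparison.

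**What to change.** For objective 3, relate RAM type to adherence change (or to increased v not increased) in a regression that adjusts for run-in adherence. Use the last RAM completed before that child's reminder was activated. Word the two groups as increased and not increased. Repeat the analysis among children with at least one missed run-in dose, and report fully adherent children separately. The adjustment is the essential part, because dropping only the children at exactly 100% leaves near-ceiling children in.

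All the data needed are already collected. The cost is a regression model alongside the chi-squared test and slightly fewer children in the repeated analysis. The SAP is written in the past tense, so if the analysis has been run, this is a short re-analysis that should be labelled as such.
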